#### RANDOMIZATION PROCESS:

We will conduct randomization using a randomized block design, ensuring that each group of 20 envelopes has 10 intervention and 10 control per block, shuffling each block to ensure a near random order. The full set of 1104 will be numbered before distribution to sites. Each group assignment envelope will be selected by the coordinator and then opened by the participant and shown to the coordinator or 2WT enrollment coordinator. Security envelopes will be used to help prevent selection of assigned group. Subjects within each block are randomly assigned to treatment conditions. This design reduces variability within treatment conditions and potential confounding, allowing for more interim analysis with near equal size groups and more certain randomization within sites.

Standard VMMC care (Control arm): For the 552 men randomized into the control arm, Aurum Institute follows all NDOH protocols based on WHO guidelines  including routine surgical VMMC follow-up on post-surgery days 2, 7 and 21 (Table 1) . Patients may seek care outside scheduled visits for suspicion of AEs at any healthcare facility at any time but most often return to their VMMC site. Referral cards for VMMC clients provide local numbers for patients to text, call, or request a call back for emergencies. A standardized approach is used to assess, identify, and record the severity of AEs . All VMMC care, from assessment of all AEs through complete healing, is provided free to clients from NDoH. Clients who do not return to the clinic for follow-up on Day 2 or Day 7 are traced: 3 attempts by phone and then 1 attempt at in-person tracking after which they are considered lost to follow-up (LTFU). There is no tracing for Day 21 visits. For the purposes of this study, control arm VMMC clients will be asked to come in on Day 14 for an additional follow-up visit. Active follow-up by phone call is provided at Day 14.

[figure not shown]
VMMC care procedures (2wT arm): We will conduct a prospective, un-blinded, randomized control trial (RCT) among VMMC clients in a 1:1 ratio of control to intervention. Study participants and clinic staff are not masked to treatment. For the 552 men randomized into the intervention arm, men in the 2wT will receive routine VMMC surgical care and counseling, including referral cards for emergencies. 2wT clients will receive automated daily texts from days 1-14 (Table 1 and Figure 3). It is free to receive call and texts; it costs approximately R0.20 to send a SMS in RSA . If they respond that they suspect no adverse event, no immediate follow-up action will be taken. If a 2wT VMMC client responds affirmatively to any daily text that he

[figure not shown]
suspects an AE, a VMMC nurse will exchange modifiable, scripted texts with the client to determine the symptoms, frequency, and severity. Then, if deemed necessary, the client will be asked to return to clinic the following day or earlier if an emergency is suspected. AE management will adhere to NDOH standard care. If 2wT patients do not respond to texts on Day 2 or Day 7, the same NDOH tracing process will be activated on Day 14, after which they will be considered LTFU. All study participants will be asked to come to the clinic for study-specific, Day 14 follow-up to review healing and verify adverse event reporting. Day 14 was chosen for verification because 95% of all AEs within a similar VMMC program in Zimbabwe are reported Day 14 or earlier 61, suggesting that most AEs have occurred by this time point. In a previous field study of AEs, the most common AEs of bleeding and infection were found a mean of 6.7 and 9.0 days, respectively, after VMMC , further supporting the 14 day period used in this and a previous study. The Day 14 review will be conducted by routine VMMC providers according to NDOH review guidelines. At Day 21, we will implement a brief text-based survey with 2wT clients to ascertain complete healing, providing stronger inferences at study completion.

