#### PARTICIPANT ELIGIBILITY AND RECRUITMENT:

VMMC client recruitment, voluntary consent, and enrollment will be managed by the on-site 2wT study coordinator before VMMC surgery. Eligibility criteria for VMMC clients are: 1) 18 years or older; 2) possession of own phone at enrollment; 3) provides contact details (phone, address, next of kin); 4) requests surgical VMMC; 5) willing to follow NDOH VMMC protocols; 6) willing to come in Day 14; 7) willing to respond to a questionnaire administered by phone 21 days after circumcision. Men without cell phones and those who chose an MC device will be excluded as devices require a device-removal visit 7 days after placement and have distinctly different follow-up protocols. As phone sharing practices are common, informed consent will ascertain whether eligible men have consistent access to a phone to receive messages about AEs. Participants who refuse enrollment will be asked to provide informed consent for data collection about reasons for non-participation. We expect to enroll and randomize men into a 1:1 ratio of intervention and control within 6 months, allowing observation of the primary outcome by end of year 1. On Day 14, all men in both arms who return for follow-up will receive a Rand 100 airtime credit.

able 2: Study procedures overview 1:		2:	3:	
	Test		Intensive	Maintain
Location	Rural & Urban		Rural	Rural
2wT-based follow-up	Randomized		Opt-in	Opt-in
Research or Routine VMMC delivery team	Research		Research	Routine
N	552	552	800	Routine
Specific Activities	Control	2wT		
Day 0 (Day of MC)				
Routine VMMC client intake forms	X	X	X	X
VMMC surgery and counseling	X	X	X	X
Study consent	X	X	X	X
Wound care/bandage removal counseling	X	X	X	X
Post-op. texting and AE counseling		X	X	X
Scheduled in-person follow-up				
Routine Day-2	X			
Routine Day-7	X			
Study-specific Day-14 (\$7 provided)	X	X		
Routine Day-21	X			
Active client follow-up				
Emergency	X	X	X	X
2wT-specific processes				
Daily texts days 1-13		X	X	X
Tracing if no SMS/phone/visit ~d14		X		
NDOH routine AE procedures				
In-person, any day, review if AE concern	X	X	X	X
Emergency VMMC after-hours care	X	X	X	X
AE identification	X	X	X	X
AE severity grading	X	X	X	X
AE management and treatment	X	X	X	X
AE reporting on routine MoHCC forms	X	X	X	X

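### The enrolling coordinator selects the envelope from fixed, shuffled blocks of 20 with no stated order-of-use rule, so up to 9.1% of allocations could be known in advance

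*Protocol*

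**What the plan says.** The Randomization Process part of protocol section 6 sets out the whole method.

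- **Sequence:** blocks of fixed size, "ensuring that each group of 20 envelopes has 10 intervention and 10 control per block, shuffling each block to ensure a near random order".
- **Numbering:** "The full set of 1104 will be numbered before distribution to sites".
- **Choice of envelope:** "Each group assignment envelope will be selected by the coordinator and then opened by the participant and shown to the coordinator". The sentence goes on to name a 2wT enrollment coordinator as an alternative person to whom the result may be shown.
- **Concealment:** "Security envelopes will be used to help prevent selection of assigned group".

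The same section states that "Study participants and clinic staff are not masked to treatment". Under Participant Eligibility and Recruitment, "VMMC client recruitment, voluntary consent, and enrollment will be managed by the on-site 2wT study coordinator before VMMC surgery". Recruitment and Informed Consent has the site study coordinator confirm eligibility and seek consent. Section 7 gives a Study Coordinator the texting database and the contact with intervention clients.

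The SAP says only that randomization is 1:1. Neither document, as shown, requires the next number to be used, requires an entry before opening, reconciles used and unused envelopes, or names an independent person to prepare or hold the sequence.

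**The concern.** Concealment in an envelope trial needs two things: nobody can see the contents, and nobody on the enrolling side can influence which man gets which envelope. The plan addresses the first. On the second it leaves selection to the coordinator. Numbering protects only if the order is compulsory and checked.

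The block is also fixed, and its size is printed in the protocol. In an unmasked trial the enrolling side sees results accumulate, and towards the end of a block the remaining split may be known. A man can then be enrolled now or asked to wait, according to the arm that is due. The coordinator meets each man and takes his contact details, so has some basis for judging who is likely to return. Return affects whether an AE is found. With so few AEs expected, a small imbalance in such men could matter, and it cannot be fully repaired at analysis.

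**Working it through.** **Inputs.** Block of 20, 10:10, and 1,104 envelopes (protocol, Randomization Process). AE ascertainment of 0.5% control and 2.0% texting, margin -0.25%, one-sided 95% limit, 80% power, 10% loss to follow-up (SAP, Sample size and power).

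**1. The plan's own sample size.**
n per group = (z₀.₉₅ + z₀.₈₀)² × [p₁(1−p₁) + p₂(1−p₂)] / (difference + margin)²
= (1.645 + 0.842)² × (0.004975 + 0.0196) / (0.015 + 0.0025)²
= 6.1826 × 0.024575 / 0.00030625 = 496.1, so 497.
Total 994, and 994/0.9 = 1,104.4. The stated 1,104 reproduces, so the sample size is not in question here.

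**2. Allocations known with certainty.** For a block of 2m with m per arm, the expected number of allocations made when only one arm remains is 2m/(m+1). With m = 10 this is 20/11 = 1.82, or 9.1% of the block. Over 1,104/20 = 55.2 blocks, 1.82 × 55.2 is about 100 men.

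**3. Best-guess accuracy.** Always naming the arm with more envelopes left gives m + [2^(2m)/C(2m, m) − 1]/2 correct guesses per block:
10 + (1,048,576/184,756 − 1)/2 = 10 + (5.675 − 1)/2 = 12.34 of 20 = 61.7%, against 50% by chance.
The excess is 2.34 × 55.2, about 129 correct guesses in 1,104.

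Steps 2 and 3 assume one person who knows the block boundaries and has seen every earlier result in the block.

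**4. Is 20 too small?** The same calculation for other fixed blocks:

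| Block | Certain | Best guess correct |
|---|---|---|
| 4 | 33.3% | 70.8% |
| 10 | 16.7% | 65.3% |
| 20 | 9.1% | 61.7% |

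Smaller fixed blocks are more predictable, so the size itself is not the weakness.

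**5. Sensitivity of the AE result.** Expected events are 497 × 0.02 = 9.9 texting and 497 × 0.005 = 2.5 control, taken as 10 v 3. The SAP names no interval method, so a Wald interval is assumed: lower limit = d − 1.645 × √{[p₁(1−p₁) + p₂(1−p₂)]/497}. Moving a case means exchanging him with a man without an AE, so both arms stay at 497.

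| AEs, texting v control | d | 1.645 × SE | Lower limit | Against -0.25% |
|---|---|---|---|---|
| 10 v 3 | 1.41% | 1.18% | +0.23% | pass |
| 9 v 4 (one moved) | 1.01% | 1.18% | -0.18% | pass |
| 8 v 5 (two moved) | 0.60% | 1.19% | -0.58% | fail |

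This shows how few men separate a pass from a fail. It does not estimate how many would be moved.

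**The case against.** The strongest defence is that the contents are hidden. If the shuffle is sound, every sealed envelope left in a block has the same chance of holding either arm, so picking among them tells the coordinator nothing beyond counting down. A reader might infer from the word selected that the coordinator can choose the arm, with no limit on the bias. The documents do not support that. Extra gain would need several blocks open at once, or opened or tampered envelopes, and neither is described. The objection stands against that reading. It does not answer the count-down, which needs only the history and a decision on when to enrol a man.

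Other points also have weight:

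- **Who sees what.** A reader might infer that one person recruits, enrols and sees every allocation. The result may instead be shown to an enrollment coordinator, and the recruitment text separates a research coordinator from the site study coordinator, although a later paragraph merges the roles. Whether blocks stay whole within a site is not stated. Both points lower the predictability figures.
- **Possible rule elsewhere.** Numbering all envelopes before distribution suggests that use in order was intended, and an unseen SOP may say so. If it does, the protocol text still needs to agree with it.
- **Masking.** Unmasked treatment is unavoidable when texting is compared with visits. It is not itself evidence of poor concealment before allocation.
- **Visit outcome.** Table 2 schedules four visits for control and one for texting. That contrast is built in, and modest steering could hardly create it. Adjusted models are planned, but they handle only measured confounders.
- **Foresight.** Moving AE cases means identifying them before surgery, which would be hard.

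**Conclusion.** The point holds as a preventable weakness in allocation concealment. It comes from three features together: a fixed and published block size, an enrolling coordinator who selects the envelope in an unmasked trial, and no shown rule on order of use or logging. At most 9.1% of allocations (about 100 of 1,104) would be known with certainty, and at most 61.7% guessed correctly. Both limits assume known boundaries and a full history within the block, and both fall if blocks are split between sites or coordinators.

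A reader might go further and infer that steering happened, that either outcome is biased by a known amount, or that one misplaced man would overturn the AE result at the planned rates. The documents show no steering, and the figures describe predictability only. At 10 v 3, one moved case still passes and two fail, given the Wald assumption. Nor do the documents say that the shuffling is done by hand; they describe only "shuffling each block to ensure a near random order".

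The change should be made before enrolment, because allocation cannot be redone afterwards.

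**What to change.** In the Randomization Process section, replace selection by the coordinator with four rules:

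1. The next-numbered envelope at that site must be used.
2. Participant ID, date and time are written on the sealed envelope and in a log before it is opened.
3. Used and unused envelopes are reconciled against the log.
4. The order comes from a computer-generated list per site, with randomly varying block sizes not disclosed to enrolling staff. This replaces the shuffling and the fixed block of 20.

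If an SOP already contains an order rule, bring the protocol into line with it.

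The cost is protocol wording, one list and a simple log. Incomplete blocks may leave a slight imbalance between arms. The present scheme has a remainder too: 55 blocks of 20 make 1,100 and leave 4 envelopes whose split is not stated. The sample size stays at 1,104.

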#### PARTICIPANT ELIGIBILITY AND RECRUITMENT:

VMMC client recruitment, voluntary consent, and enrollment will be managed by the on-site 2wT study coordinator before VMMC surgery. Eligibility criteria for VMMC clients are: 1) 18 years or older; 2) possession of own phone at enrollment; 3) provides contact details (phone, address, next of kin); 4) requests surgical VMMC; 5) willing to follow NDOH VMMC protocols; 6) willing to come in Day 14; 7) willing to respond to a questionnaire administered by phone 21 days after circumcision. Men without cell phones and those who chose an MC device will be excluded as devices require a device-removal visit 7 days after placement and have distinctly different follow-up protocols. As phone sharing practices are common, informed consent will ascertain whether eligible men have consistent access to a phone to receive messages about AEs. Participants who refuse enrollment will be asked to provide informed consent for data collection about reasons for non-participation. We expect to enroll and randomize men into a 1:1 ratio of intervention and control within 6 months, allowing observation of the primary outcome by end of year 1. On Day 14, all men in both arms who return for follow-up will receive a Rand 100 airtime credit.

able 2: Study procedures overview 1:		2:	3:	
	Test		Intensive	Maintain
Location	Rural & Urban		Rural	Rural
2wT-based follow-up	Randomized		Opt-in	Opt-in
Research or Routine VMMC delivery team	Research		Research	Routine
N	552	552	800	Routine
Specific Activities	Control	2wT		
Day 0 (Day of MC)				
Routine VMMC client intake forms	X	X	X	X
VMMC surgery and counseling	X	X	X	X
Study consent	X	X	X	X
Wound care/bandage removal counseling	X	X	X	X
Post-op. texting and AE counseling		X	X	X
Scheduled in-person follow-up				
Routine Day-2	X			
Routine Day-7	X			
Study-specific Day-14 (\$7 provided)	X	X		
Routine Day-21	X			
Active client follow-up				
Emergency	X	X	X	X
2wT-specific processes				
Daily texts days 1-13		X	X	X
Tracing if no SMS/phone/visit ~d14		X		
NDOH routine AE procedures				
In-person, any day, review if AE concern	X	X	X	X
Emergency VMMC after-hours care	X	X	X	X
AE identification	X	X	X	X
AE severity grading	X	X	X	X
AE management and treatment	X	X	X	X
AE reporting on routine MoHCC forms	X	X	X	X

#### 7. TRAINING OF STUDY PERSONNEL:

VMMC staff at Aurum Institute study sites will be informed of the study and briefed on study protocols. A 2wT study coordinator will be trained in confidentiality, protection of human subjects, enrollment, and data collection methods, working to not interfere with routine VMMC flow. For technology training, an experienced Medic Mobile trainer from Nairobi will work with the local study coordinator and team members in-person to implement and learn to maintain the Medic Mobile toolkit independently. We believe that achieving local maintenance and ownership of the system is feasible because of Medic Mobile's considerable investments in open source collaboration and in designing software that is user friendly and intuitive enough to be adapted and maintained by local staff. As part of 2wT, one experienced Aurum Institute VMMC nurse will serve as Study Coordinator in Pietermaritzburg and will manage the texting database, including text and voice follow-up communication with intervention clients. RSA-based co-investigators and interested partner organization researchers will also be invited for Medic Mobile training.

#### 8. Study Participants:

Group name/description	Data collection method	Age range of subjects	Target number of individuals
Men in the intervention pilot (texting): Assigned texting	Usability survey, routine VMMC clinical review	18-6 5	50
Men in intervention group (texting):  Randomized into group	Interview , routine VMMC clinical review	18-6 5	552(100 selected for the satisfaction and acceptability questionnaires )
Men in control group (routine care): Randomized into group	Routine VMMC clinical review	18-6 5	552
Healthcare workers (VMMC clinicians)	Interview	18-6 5	~10

#### 9. Data collection:

Sample size:

#### 10. DATA ANALYSIS:

For Objective 1, the 2wT safety outcome of interest is cumulative AE rate (moderate or severe) ≤ Day 14. In RSA, and similar to other countries in the region. moderate AEs are those which include symptoms requiring modification of activity, but not resulting in loss of work or cancellation of social activities while severe AEs are those with incapacitating symptoms, requiring bed rest and loss of work 66. Incidence of AEs before Day 14 will be extracted from routine VMMC data for both 2wT and control. Incident AEs on Day 14 will be identified, classified, and graded for severity using routine NDOH protocols  and recorded on routine VMMC AE forms. We will compare cumulative rates of any moderate or severe AE ≤ Day 14 between groups using Fisher's exact test as the expected number of AEs is low. The rates will be calculated per arm as: (# moderate + severe AEs)/ (total # VMMC clients who attend/responded to 2, 7 or 14 Day follow-up visits or texts). Multivariate logistic regression models (any AE v none) will quantify the magnitude of difference, adjusting for any potential confounders. To determine follow-up visit reduction, we will compare the mean number of in-person visits for intervention and control using a t-test. A multivariate linear regression model will further quantify the effect of intervention on visit reduction, adjusting for potential confounders. Secondary outcomes include: AE rates on Day 14, texting response rate, time between 2wT AE text reporting and follow-up, severity of AEs. We will perform appropriate summaries of missing data and LTFU, testing for systematic differences in response by study arm. We hypothesize that 1) 2wT is non-inferior to routine follow-up for patient safety and that 2) 2wT will reduce unnecessary follow-up over standard care.

For Objective 2, 2wT costs, we will calculate the relative costs and outcomes (effects) of intervention versus control, including costs for technology, healthcare worker time, and client considerations (travel, text costs, missed work). We will conduct both activity-based costing from the implementation perspective and from the technology perspective to extrapolate our results as costs that would be incurred by the NDOH should they elect widespread scale up of 2wT. Approach for costing. First we quantify the total direct and indirect costs of 2wT deployment, a method previously used for technology cost assessment in Malawi 48, which includes comprehensive costs from installation and training, routine maintenance, healthcare worker time associated with 2wT, and staff efficiency gains/losses in addition to the direct cost of technology. Second, we will estimate incremental costs (incremental relative to standard practice) for the intervention. This component entails a micro-costing study using activity-based approaches for costs incurred (trainings. VMMC service provision, follow-up) and costs averted (health costs for providers and patients saved by reducing visits), adapting previous VMMC costing estimates 67 for 2017 dollars when appropriate. Cost data will also be collected from the study budget, public health clinic budgets, published government reports, and the health economics literature. Lastly, to estimate the cost savings associated with 2wT over routine VMMC follow-up, we will conduct a time-motion study  to quantify time spent for VMMC follow-up, indicating potential time savings for providers and VMMC clients. One trained observer will record VMMC client/provider follow-up interactions for 5-10 days, or approximately 100 reviews, recording times and activities using a pre-established checklist and timing system. During these same 5-10 days, client

time from registration through visit completion will be recorded by a second observer. Data will be exported into STATA 12.0 for analysis. The combined, overall costs for the delivery of 2wT in public health clinics will be estimated and compared to standard follow-up. We hypothesize that 2wT will reduce the costs associated with VMMC patient follow-up over standard care.

For Objective 3, 2wT acceptability, using study recruitment and enrollment logs in addition to the texting database, we will describe levels of acceptance, participation, refusal and drop-out. We will carry out key informant interviews (KIIs) with up to 10 health care workers to gauge acceptability, satisfaction, identify facilitators and barriers to program success, and ascertain suggestions for intervention improvement. KIIs will be audio recorded and transcribed. Atlas.Ti software will be used to create a spreadsheet of key themes, perceived barriers, and suggested facilitators to the program from KIIs. We will also implement questionnaires at the Day 14 visit with a subset of 100 2wT VMMC clients in the main study who were randomized to texting to gauge satisfaction, estimate direct and indirect costs (time away from work, transportation costs), and ascertain suggestions for intervention improvement. Responses from these brief. self-administered, quantitative surveys with VMMC clients will be entered in Excel and frequencies explored in STATA 12.0. For feasibility, costing data will be combined with usability and acceptability information. These comprehensive data will be discussed at a final stakeholder meeting to disseminate study results, validate interpretations and refine recommendations for future scale up and modification of 2wT in RSA and beyond. Additional meetings between local researchers and the NDOH will further determine feasibility for replication and scale-up. We hypothesize that acceptability, usability, and feasibility will be high, aiding program scalability.

